## **Statistical Analysis Plan**

Descriptive statistics (frequencies, means, standard deviations) will summarize the caregiver and patient characteristics and program implementation costs. A generalized linear model (GLM) will test for significant differences between the control and intervention groups in terms of health outcome scores measured at baseline and at 3 and 6 months, controlling for covariate effects. The GLM is the extended version of the general linear model applicable to variables that are not normally distributed and is commonly used in small sample studies [39]. The GLM also provides a post hoc analysis that yields results similar to those of t tests. A strength of GLM is that it also provides repeated data collection time factors in post hoc analyses. A one-tailed group comparisons will be used to test our *a priori* directional hypotheses using the

---

Bonferroni adjustment. [40]. Thus, this post hoc paired comparison between groups can reveal significant differences between outcomes at baseline vs. 3 months and at baseline vs. 6 months. The intent-to-treat statistical approach will be used, as all patients are included in the analysis with imputation means replacement [41]. Data analyses will be conducted using SPSS (version 29).

This study will use a traditional cost accounting method to calculate the cost of implementing FamPALcare. All expenses related to delivering the program will be tabulated. The cost of the clinician delivering the intervention will be calculated from an average of a nurse's hourly salary. The costs of educational materials given to participants in the manual will be tallied and summarized.

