## Objectives

The following specific aims, directional hypotheses, and research questions are:

**Primary Aim:** To test whether the FamPALcare nursing care intervention could reduce the burden of family caregivers by preventing caregiver depression/anxiety and improve patient HF-related health status and depression/anxiety. The hypotheses and research questions are as follows:

*Aim 1.1* Compared to those in the control group at 3 and 6 months, the caregivers who receive FamPALcare will have significant improvements in home caregiving burden and depression/anxiety scores.

*Aim 1.2* Compared to those in the control group at 3 and 6 months, patients in the FamPALcare group will experience greater improvement in HF-related health and depression/anxiety scores.

**Secondary Aim:** To assess the feasibility and fidelity of the FamPALcare intervention.

*Aim 2.1.* What are the participant recruitment, enrollment, and retention outcomes?

*Aim 2.2.* How helpful the FamPALcare as rated by participants on the anonymous 11-item Helpfulness Questionnaire?

*Aim 2.3.* What is the FamPALcare implementation cost using traditional tabulated cost-minimization analysis?

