### *Randomization and Blinding*

This RCT uses random assignment to group with stratification of the patient sex (male vs female) to equalize distribution. SPSS version 29 is used to generate random numbers within each group. Each family dyad is randomly assigned to either the control or intervention group in a 1:1 fashion [11]. The researchers are blinded to the group assignments until informed consent is obtained. The Institutional Review Board of the University Health Sciences Center (WVU IRB 1709754988) approved the study protocol.

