## **Statistical Considerations**

### ***Sample Size Calculation***

In this R15, sample size is based on reductions in breathlessness; a significant reduction of 1 SD, was found in the PI's previous interventions on end-stage HF breathlessness. A sample size of 30 (15 per group) is able to detect a reduction of 1.3 SDs with a Type 1 error rate of 0.05 and a power of 0.80 [31-33] To account for an expected 20% attrition (due to HF deaths), three additional families will be recruited to each group. Thus, there will be 18 patient-caregiver dyads per each group (total N=72; 36 patients and 36 caregivers).

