## **Data Management**

### ***Data Collection Methods***

Data will be collected from all patients and caregivers at baseline, 3 months, and 6 months. The analyses file of this project will include repeated questionnaire variables across 3 time points, including caregiver and patients' sociodemographic health data.

To preclude diffusion of treatment across groups, the research nurses working with the intervention group will be different from nurses with the control group. Data collectors are blinded to group. Secure data collection and storage is maintained. A home HF EOLPC checklist is used to assess at 3, 6, and 12 months the home care skills learned by the caregiver and to identify areas that may need reinforcement.

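### The planned baseline-versus-follow-up comparison should be fixed as a baseline-adjusted group difference at 3 and at 6 months; read as unadjusted change it gives up precision at no benefit

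*Combined protocol and SAP*

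**What the plan says.** The Statistical Analysis Plan section of the combined protocol and SAP specifies a generalized linear model comparing the two groups on "health outcome scores measured at baseline and at 3 and 6 months, controlling for covariate effects". Baseline is therefore listed as one of three outcome times, and the covariates are not named. The section then says that "this post hoc paired comparison between groups can reveal significant differences between outcomes at baseline vs. 3 months and at baseline vs. 6 months". Tests are one-tailed with a Bonferroni adjustment whose divisor is not given.

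Other sections bear on the same point:

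- Objectives, Aim 1.1: "Compared to those in the control group at 3 and 6 months, the caregivers who receive FamPALcare" are expected to show better burden and depression/anxiety scores. Aim 1.2 has the same form for patients. Both are group comparisons at the follow-up visits.
- Randomization and Blinding: allocation is 1:1 by dyad, with "stratification of the patient sex (male vs female) to equalize distribution".
- Sample Size Calculation: 15 per group is said to be "able to detect a reduction of 1.3 SDs with a Type 1 error rate of 0.05 and a power of 0.80". An earlier effect of 1 SD on breathlessness is also cited.
- Data Collection Methods: "The analyses file of this project will include repeated questionnaire variables across 3 time points", so baseline scores will be on file.

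**The concern.** The text leaves the Aim 1 test open to three readings:

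1. **Group difference in change from baseline, without baseline adjustment.** This is the most natural reading of a paired comparison between groups when baseline is an outcome time.
2. **Baseline versus follow-up within each arm.** The word paired allows this. Such a test does not compare the arms.
3. **Group difference in the 3- and 6-month scores with baseline among the unnamed covariates.** This matches the aims and loses nothing.

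Under reading 1 the stake is precision. A change score subtracts the whole baseline value. Adjustment subtracts only the part that predicts follow-up, so it carries less noise unless the correlation is very high. With about 15 dyads per arm and a Bonferroni-adjusted test, that can be worth several dyads. Under reading 2 the stake is greater, because improvement common to both arms could be taken for an intervention effect.

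Adding baseline to the covariate list is not enough if baseline also stays an outcome time, as shown below.

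**Working it through.** **Inputs from the documents.** 15 analysed per arm; 1 SD and 1.3 SD effects; alpha 0.05 (Sample Size Calculation); one-tailed, Bonferroni (Statistical Analysis Plan).

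**Assumed, not in the documents.** Baseline-to-follow-up correlation ρ from 0.3 to 0.9; equal SDs at all visits; effects in raw-score SD units; 15 per arm for patients and caregivers alike; observed scores only; Bonferroni divisor 1 or 8. The 8 is four scores (caregiver burden, patient HF-related health, and one depression/anxiety score for each person) × two visits.

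**The plan's own figure.** For an unadjusted two-sample t test of 1.3 SD at 80% power, the noncentral t gives 11 per group two-sided or 9 one-sided, not 15. With 15 per group, power is 93% two-sided and 97% one-sided. Exactly 15 is reached with one-sided 0.05/8 = 0.00625 (power 80.6%), a divisor the plan does not state. The stated size is thus conservative for its stated inputs, and the comparison below does not depend on it.

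**Variance of the group difference** (SD = 1, n = 15 per arm):

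- Change: 4(1 − ρ)/n.
- Adjusted: 2(1 − ρ²)/n × [1 + 1/(2n − 4)], where the bracket is 1 + 1/26 = 1.038, the cost of estimating the slope.
- Ratio, adjusted to change: (1 + ρ)/2 × 1.038.

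At ρ = 0.5, change gives 4 × 0.5/15 = 0.133 and adjusted gives 2 × 0.75/15 × 1.038 = 0.104, a ratio of 0.779. The equivalent number of extra dyads is 30 × (1/ratio − 1).

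| ρ | Ratio | Variance reduction | Extra dyads on 30 |
|---|---|---|---|
| 0.3 | 0.675 | 32% | about 14 |
| 0.5 | 0.779 | 22% | 8 to 9 |
| 0.7 | 0.883 | 12% | 4 |
| 0.9 | 0.987 | 1% | under 1 |

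The gain vanishes where (1 + ρ)/2 = 1/1.038, at ρ of about 0.93.

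**Power** (noncentral t; 28 df for change, 27 for adjusted), change → adjusted:

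| ρ | 1 SD, one-sided 0.05 | 1 SD, one-sided 0.00625 | 1.3 SD, one-sided 0.05 | 1.3 SD, one-sided 0.00625 |
|---|---|---|---|---|
| 0.3 | 73 → 86% | 38 → 56% | 90 → 97% | 63 → 83% |
| 0.5 | 85 → 92% | 53.5 → 66.5% | 97 → 99% | 81 → 90% |
| 0.7 | 96 → 98% | 80 → 85% | 99.8 → 99.9% | 97 → 98% |

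**Validity.** In simulation with 15 per arm, both estimators were unbiased for a true 1 SD effect, and both had one-sided type I error of 4.9 to 5.1% at nominal 5%.

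**Baseline as both outcome and covariate.** A main-effect covariate adds the same term γ × baseline to a person's score at every visit. It cancels when baseline is subtracted from follow-up. With complete data and an independent or exchangeable working correlation, the group contrast then equals the unadjusted change. A three-visit simulation at ρ = 0.5 confirmed this to within rounding (10⁻¹⁴).

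**Within-arm reading.** Assume a 0.5 SD improvement common to both arms and no treatment effect. A one-sided within-arm test at 0.05 was significant in 46% (ρ = 0.3) to 77% (ρ = 0.7) of simulated trials.

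**The case against.** The strongest reply is that the plan never says the analysis is unadjusted. It promises covariate control in a between-group model, and baseline may be one of the covariates. That stands: the loss is conditional, and a reader who infers that the plan omits baseline adjustment goes beyond the text. The reply does not remove the point. The section also keeps baseline as an outcome time, and in that structure a baseline main effect changes nothing in the contrast described.

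A second reply is that the gain is often small. This also stands in part. For 1.3 SD before Bonferroni, the change test has at least 90% power at every ρ shown and gains little from ρ = 0.5 up. The larger losses need a low or moderate ρ combined with the 1 SD effect or a large divisor.

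Third, the power figures read the SDs as raw-score SDs, which the Sample Size Calculation section does not specify. If they are SDs of change, the change test has 85% power for 1 SD and 97% for 1.3 SD at one-sided 0.05, whatever ρ is. The variance ratios are unaffected. The cited effect also concerns breathlessness, which Aims 1.1 and 1.2 do not name, and the attrition allowance is for patient deaths, so 15 per arm may not fit caregivers.

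A reader might also infer bias or an inflated type I error. For the between-group change contrast with complete data, neither arises.

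**Conclusion.** The point holds as one of precision and clear specification. Read as a between-group difference in unadjusted change, the planned test is unbiased and holds its level with complete data. It gives up about 32%, 22%, 12% or 1% of variance at ρ = 0.3, 0.5, 0.7 or 0.9, relative to a baseline-adjusted comparison that answers the stated aims with data already being collected. These figures rest on the assumed ρ and equal SDs across visits; the powers rest also on raw-score SD units, the divisor, and 15 per arm for both members of the dyad.

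Read as within-arm tests, the comparison does not address the treatment effect. Read as baseline-adjusted follow-up scores, it needs only clearer wording. The documents do not settle which is meant, so they do not support calling the analysis invalid or the trial underpowered on this ground.

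The plan's mean replacement of missing scores ("all patients are included in the analysis with imputation means replacement") and the handling of scores after a patient's death are separate questions. The precision figures here apply to observed scores.

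**What to change.** State in the Statistical Analysis Plan section:

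> The Aim 1 tests are the between-group differences at 3 months and at 6 months. Each is adjusted for the baseline score of the same outcome and for patient sex. Baseline enters as a covariate and is not also an outcome time. Its slope may differ by visit, through a baseline-by-time term or a separate model for each visit. Within-arm comparisons of baseline with follow-up are descriptive.

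Sex is included because randomisation is stratified by it. All this can stay within the planned GLM in SPSS.

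An acceptable alternative is a longitudinal model of all three visits, with baseline means held equal across arms and a small-sample correction. In a simpler check with one follow-up visit and no sex term, the uncorrected version had one-sided type I error of about 5.6%. With sex and three visits, its estimates are similar but not identical to those of the adjusted analysis: they differed from a per-visit adjusted analysis by up to 0.24 to 0.29 SD in single simulated trials. Participants with baseline data only moved its estimates by up to 0.02 to 0.06 SD. One of the two should therefore be chosen in advance.

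The cost is SAP wording and one or two degrees of freedom. Adding sex moves power for 1 SD from 66.5% to 66.2% at ρ = 0.5 and divisor 8. No new data or software is needed.

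### The generalized linear model named for three repeated scores leaves within-person correlation unspecified; fitted as named, it loses power on the change-from-baseline contrasts

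*Combined protocol and SAP*

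**What the plan says.** The Statistical Analysis Plan section names the model for the primary aims: "A generalized linear model (GLM) will test for significant differences between the control and intervention groups", applied to scores at baseline, 3 months and 6 months. It presents this model as an extension of the general linear model for non-normal variables, so the two are expressly distinguished.

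The scores are repeated on the same people. Data Collection Methods states: "Data will be collected from all patients and caregivers at baseline, 3 months, and 6 months", and also: "The analyses file of this project will include repeated questionnaire variables across 3 time points".

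On how the repetition is handled, the plan offers two statements. The first is "A strength of GLM is that it also provides repeated data collection time factors in post hoc analyses". The second describes the contrasts: "this post hoc paired comparison between groups can reveal significant differences between outcomes at baseline vs. 3 months and at baseline vs. 6 months".

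The hypotheses are about improvement relative to control. Aim 1.1 reads "Compared to those in the control group at 3 and 6 months, the caregivers who receive FamPALcare will have significant improvements", and Aim 1.2 is the parallel statement for patients. Tests are one-sided ("A one-tailed group comparisons will be used to test our" directional hypotheses) with a "Bonferroni adjustment" whose number of tests is not given.

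No section mentions a person-level random effect, a subject identifier, a covariance structure, a working correlation, GEE or an SPSS procedure.

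**The concern.** A generalized linear model, as named, assumes that every row of data is an independent observation. Adding time as a factor lets the mean differ between visits but leaves that assumption in place. Calling the comparison paired does not fill the gap either: the two groups contain different people, and the phrase does not say how one person's scores are linked.

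The consequence depends on the contrast. A person's own baseline normally removes between-person variation from a change score. A model that ignores the link does not take this gain, so its standard error for change is too large and real effects are missed. An average over visits goes the other way: the model counts three correlated scores as three independent ones. In a trial of 36 dyads, precision on the change contrasts is worth protecting.

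Even if a repeated-measures analysis is intended, the text does not fix it. Two analysts following it could report standard errors for the same change contrast that differ by 20% to 83%.

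**Working it through.** **The plan's own figures.** The plan gives no standard error and no within-person correlation, so there is nothing to reproduce directly. The nearest figure is 15 per group for 1.3 SD at 0.05 and 80% power (Sample Size Calculation). It does not follow from its stated inputs: a two-group t test needs 9 per group one-sided or 11 two-sided. That is a separate matter; here 15 and 1.3 SD serve only as inputs.

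**Inputs.**
- From the documents: n = 15 per group; three visits; one-tailed 0.05; effects of 1 SD (cited from earlier work) and 1.3 SD (planned).
- Assumed: equal SD of 1 at each visit; the same correlation r between any two visits, with r = 0.3, 0.5 or 0.7; the 1 and 1.3 SD effects apply to the difference in change; no Bonferroni adjustment, covariates or missing data.

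**Group difference in change from baseline (group-by-time).**
- True variance: 4(1 − r)/n. Independence variance: 4/n.
- Ratio of independence to true standard error: 1/√(1 − r).
- Independence standard error: √(4/15) = 0.516. A result is significant when the observed difference exceeds about 1.645 × 0.516 = 0.849 SD, whatever r is.
- Type I error ≈ P(Z > 1.645 × ratio).
- Power for difference d ≈ Φ((d − 0.849)/true SE) under independence, and Φ(d/true SE − 1.645) when correlation is modelled.

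Example at r = 0.5, d = 1: (1 − 0.849)/0.365 = 0.41, so power is about 66%. With correlation modelled, 1/0.365 − 1.645 = 1.09, so about 86%.

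The error rates and powers below come from simulation with t critical values (84 degrees of freedom for the independence model). A repeat run agreed within about one percentage point on power.

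| | r = 0.3 | r = 0.5 | r = 0.7 |
|---|---|---|---|
| True SE | 0.432 | 0.365 | 0.283 |
| Independence SE / true SE | 1.20 | 1.41 | 1.83 |
| Type I error (nominal 0.05) | 0.024 | 0.011 | 0.002 |
| Power, 1 SD: independence | 63% | 66% | 69% |
| Power, 1 SD: correlation modelled | 74% | 85% | 97% |
| Power, 1.3 SD: independence | 85% | 88% | 93% |
| Power, 1.3 SD: correlation modelled | 90% | 97% | near 100% |

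At r = 0.5 the difference detectable with 80% power is (1.645 + 0.842) × 0.365 = 0.91 SD when correlation is modelled, and 0.849 + 0.842 × 0.365 = 1.16 SD under independence.

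If the contrast is read as change within one group, the type I error is nearly the same as in the table.

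**Group effect averaged over all three visits.**
- True variance: (2/n)(1 + 2r)/3. Independence variance: 2/(3n).
- The independence SE is √(2/45) = 0.211, against a true 0.267, 0.298 and 0.327.
- The ratio is 1/√(1 + 2r) = 0.79, 0.71 and 0.65.
- Type I error is 0.097, 0.122 and about 0.145.

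**Group difference at one visit.** Each person contributes one score, so the ratio is 1 and the simulated type I error is 0.05.

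**The case against.** **The plan does not say the scores are independent.** A reader might infer that it commits to an analysis ignoring the repetition. The documents do not support that. They are silent on correlation, and their references to repeated time factors and paired comparison suggest that some repeated-measures handling was intended. This stands, so the finding is conditional: the standard errors are wrong if the model is fitted as named. Against the charitable reading, the section expressly separates its model from the general linear model, so it cannot simply be taken as repeated-measures ANOVA.

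**False positives.** A reader might also infer that the primary tests are declared significant too often. That is not shown. Inflation arises only for a group effect averaged over visits, baseline included, which the plan does not spell out. The contrasts it does spell out become conservative.

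**Size at the design effect.** At 1.3 SD, unadjusted power stays above the planned 80% even under independence, so it would be wrong to say that the trial fails on its own terms. This also stands, with a limit. A Bonferroni adjustment for two contrasts (an assumption, as the number is not stated) brings the independence model to 74%, 77% and 82%. A t test on change scores (28 degrees of freedom, noncentrality 1.3/true SE, one-sided 0.025) gives about 83%, 93% and 99%.

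**Omitted features.** The section also mentions covariates and mean imputation. If baseline is a covariate rather than one of the outcomes, the three-score calculation no longer applies. The covariates are not listed, so this cannot be settled from the documents.

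**Conclusion.** The concern holds as a gap in specification with a real conditional cost. The plan names a model that, fitted as named, treats three scores on one person as independent, and nothing elsewhere corrects this.

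For the group difference in change, the standard error would be 20% to 83% too large. Power would fall by about 11 to 28 percentage points at 1 SD, and by about 5 to 9 points at 1.3 SD. The type I error would be well below nominal.

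The direction follows from algebra for any positive correlation. The size rests on the assumed range of 0.3 to 0.7, equal variances, a common correlation, 15 completers per group and no adjustment for multiplicity or covariates. The point should be settled before analysis because it concerns the only inferential method given for Aims 1.1 and 1.2.

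**What to change.** In the Statistical Analysis Plan section, replace the generalized linear model by an analysis that accounts for within-person correlation, run separately for patients and caregivers. Any one of these would do:

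- A linear mixed model for repeated measures, available in the SPSS already named: person as subject; group, time and group-by-time as fixed effects; unstructured covariance over visits; Satterthwaite degrees of freedom.
- Baseline-adjusted ANCOVA at each follow-up visit. This uses one outcome per person and so needs no covariance model.
- For scores that need a non-normal model, GEE clustered on person with a small-sample correction to the standard errors.

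State which is chosen, and name the group contrasts at 3 and at 6 months as the tests of Aims 1.1 and 1.2.

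The cost is SAP wording. The mixed model estimates a few extra covariance parameters, a modest burden at this sample size. No new data, participants or software are needed.

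### The single-step Bonferroni adjustment is valid, but Holm's step-down form gives the same family-wise protection and is never less powerful; the gain depends on assumptions the plan does not state

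*Combined protocol and SAP*

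**What the plan says.** The Statistical Analysis Plan section states "A one-tailed group comparisons will be used to test our" directional hypotheses, and names the method as "Bonferroni adjustment. [40]. Thus, this post hoc paired comparison between groups can reveal significant differences between outcomes". The contrasts named beside it are the changes from baseline at 3 months and at 6 months. The section does not say how many comparisons share the adjustment, and it mentions no sequential variant.

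The hypotheses are in the Objectives section. Aim 1.1 predicts that "the caregivers who receive FamPALcare will have significant improvements in home caregiving burden and depression/anxiety scores". Aim 1.2 predicts that "patients in the FamPALcare group will experience greater improvement in HF-related health and depression/anxiety scores". Both apply at 3 and 6 months. If depression/anxiety is counted as one score per person, that is 2 caregiver outcomes and 2 patient outcomes at 2 times each, or 8 directional comparisons.

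The Sample Size Calculation section says "A sample size of 30 (15 per group) is able to detect a reduction of 1.3 SDs with a Type 1 error rate of 0.05", with power 0.80. It mentions no multiplicity adjustment. Its basis is that "a significant reduction of 1 SD, was found in the PI's previous interventions on end-stage HF breathlessness".

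**The concern.** Single-step Bonferroni compares every p-value with 0.05/m, where m is the number of tests in the family. Holm's procedure keeps 0.05/m for the smallest p-value and relaxes the threshold after each rejection. Its family-wise guarantee is the same whatever the correlation between tests, so the single-step form gives up some power with no gain in error control.

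This matters most when many of the hypotheses are expected to be true together, as Aims 1.1 and 1.2 expect, and when the sample is small. At stake is how many of the predicted improvements the trial can support. No result would be biased, and no error rate is exceeded under the present plan.

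**Working it through.** **Inputs from the documents.** 15 evaluable per group, 0.05 Type 1 error, 1.3 SD detectable effect and 1 SD earlier effect on breathlessness (Sample Size Calculation); 1:1 allocation by dyad (Randomization and Blinding); one-tailed tests and two time contrasts (Statistical Analysis Plan); four outcomes (Objectives).

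**Assumptions not in the documents.** Family sizes m = 2, 4 and 8; correlation 0.6 between times and 0.4 between outcomes (0.4 × 0.6 = 0.24 for different outcomes at different times); effect sizes as shown. A two-sample t test stands in for the planned model contrast.

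**The plan's own figure.** The noncentrality is 1.3 × √(15/2) = 3.56 on 28 degrees of freedom. Power at 0.05 is 0.966 one-sided and 0.93 two-sided, not 0.80. A value near 0.80 appears only if alpha is split, for example 0.806 at one-sided 0.05/8. The documents state no split. They give no power under either multiplicity method, so there is no stated figure to compare with the results below.

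**The two rules.** Bonferroni rejects hypothesis i if p(i) ≤ 0.05/m. Holm orders the p-values from smallest to largest and rejects in turn while the j-th satisfies p ≤ 0.05/(m − j + 1), stopping at the first failure. For m = 2 the Holm thresholds are 0.025 and then 0.05. For m = 8 they run from 0.00625 up to 0.05. No Holm threshold is below 0.05/m, so every Bonferroni rejection is also a Holm rejection. Both methods make a first rejection only if the smallest p-value is at most 0.05/m, so the chance of at least one rejection is identical.

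**Bonferroni power per test at 1.0 SD.** The noncentrality is 1.0 × √(15/2) = 2.739. The critical values are 2.048 (m = 2), 2.368 (m = 4) and 2.669 (m = 8), giving power 0.753, 0.646 and 0.535.

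**Bonferroni against Holm.** Simulation of correlated t tests, 15 per group, one-tailed, 40,000 trials per row:

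| Tests | Real effects | Bonferroni | Holm | Gain (points) |
|---|---|---|---|---|
| 2 | both, 1.3 SD | 93.1% | 95.8% | about 3 |
| 2 | both, 1.0 SD | 75.4% | 81.0% | about 6 |
| 4 | all, 1.0 SD | 64.7% | 75.8% | about 11 |
| 8 | all, 1.0 SD | 53.7% | 67.4% | about 14 |
| 8 | 4 of 8, 1.0 SD | 53.5% | 57.4% | about 4 |
| 8 | all, 0.5 SD | 11.5% | 13.8% | about 2 |
| 8 | all, 0.3 SD | 4.3% | 4.8% | under 1 |

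The percentages are average power over the real effects. The Bonferroni figures at 1.0 SD agree with the exact values above.

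**All hypotheses supported, effects 1.0 SD.** 64% rises to 75% (2 tests), 31% to 58% (4) and 8% to 38% (8).

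**Error control.** With no real effects the family-wise error is the same for both methods, 0.041 to 0.044. With 4 of 8 effects real it is 0.023 for Bonferroni and 0.037 for Holm, both below 0.05.

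**Intervals.** Each additional Holm rejection has p > 0.05/m, so the matching one-sided Bonferroni interval includes zero. In the 8-test, 1.0 SD case the share is (67.4 − 53.7)/67.4 = 0.20, or about one in five Holm rejections.

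**The case against.** The strongest reply is that nothing here is wrong. Bonferroni is prespecified, valid and conservative, and it contradicts nothing else in the plan. That stands. A reader might infer that the plan contains an error, but the documents do not support that.

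A reader might also take 14 points as the power the plan loses. The documents do not support that either. It needs a family of eight, while the plan defines no family and names only two time contrasts beside the adjustment. It also needs all eight effects to be real at 1 SD, a size reported only for breathlessness, which is not named in Aims 1.1 or 1.2. Nor is 14 a bound: with independent tests, 8 effects of 1.1 SD give 16.9 points.

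A third inference is that Bonferroni makes support for the full set of hypotheses unlikely and that Holm cures this. With two tests at 1.0 SD, Bonferroni already gives 64%. With eight, Holm still gives only 38%. At 0.5 SD or below, eight tests have low power under either method.

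Finally, the sample-size power of 0.80 is close to what one-sided 0.05/8 would give, so a reader might infer that an eight-test Bonferroni adjustment was built in. The text does not say so, and one numerical match does not establish it.

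The interval mismatch is a genuine cost. It is the same quantity as the power gain, so it cannot be called rare where the gain is large. None of this removes the basic ordering: for any family of two or more tests, Holm rejects at least as much under the same guarantee.

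**Conclusion.** The point holds as an optional improvement in efficiency. The ordering of the two methods is exact and needs no assumption about the family, the effects or the correlations. The size of the gain does need them. For the two contrasts the plan names it is about 3 to 6 points at effects of 1.3 to 1.0 SD. For eight tests it ranges from about 14 points, if every effect is real at 1.0 SD, to 4 if half are, and to 2 or less at 0.5 SD or below. These figures rest on 15 evaluable per group, one-tailed t tests and the assumed correlations. The plan's undefined family is a separate matter. It decides where in this range the trial lies, but not which method is the more powerful.

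**What to change.** In the Statistical Analysis Plan section, replace the Bonferroni wording with *Holm step-down Bonferroni adjustment, applied to the ordered p-values of the prespecified group contrasts*. Make the change before any outcome data are seen by group. The Adverse Event Reporting section schedules interim data analysis reports at the bi-annual safety committee meetings, so the date of the change should be recorded against those.

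Report Holm-adjusted p-values for the decisions. If Bonferroni intervals are kept for the estimates, label them as not matching the step-down decisions, and say that each additional Holm rejection will have a matching Bonferroni interval that includes zero.

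The cost is a change of wording. It needs no new data, model or participants, and the family-wise guarantee is unchanged. The price is the interval mismatch, which grows with the gain.
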